7.4 Secondary Study Outcomes

Absence of secondary reintervention

Time to hospital discharge

7.6 Identification of Source Data

The study data will be captured and recorded on paper source documents.

8 Subject Selection Enrollment and Withdrawal

8.1 Inclusion Criteria

1. Patients undergoing a scheduled elective coaxial biopsy procedures on areas that include, but are not limited to, liver, kidney, lungs, breasts, soft tissue, etc.,
2. Patients have signed an informed consent
3. Patients who are ≥ 18 years of age.

8.2 Exclusion Criteria

1. Patients with known bleeding disorder
2. Significant congenital anomaly or medical problem that in the opinion of the investigator would preclude enrollment in this study.
3. Women of child bearing potential who are pregnant, lactating, or planning to become pregnant during the course of the clinical investigation.
4. Active systemic infection or sepsis.

8.3 Subject Recruitment, Enrollment and Screening

Subjects will be enrolled from the research centers. The study has an accrual target of at least 20 patients. The initial accrual period will last up to three months. Patients will be provided with an IRB approved Research Participant Informed Consent Form and Privacy Authorization Form describing the study devices, protocol, inclusion and exclusion criteria, as well as risks and benefits of participation.

8.4. Early Withdrawal of Subjects

Patients are free to withdraw at any time and for whatever reason. If patient withdraws consent prior to the biopsy procedure, the study data will not be collected. If patient withdraws consent after study data was already completed, the participant will need to provide instructions to the study team to remove his/her data from the data set. Pre-specified reasons for discontinuing include, but are not limited to, the following:

1. Patient Request: Patient decided that he/she did not want to continue (for any reason)
2. Adverse Event: Patient experienced a related or unrelated event that would interfere with the study objectives/evaluation
3. Inclusion/Exclusion Discrepancy/Violation: Patient should not have been enrolled
4. Other: Any other reason

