IB	Investigator's Brochure
IRB	Institutional Review Board
Non-UPIRTSO	Non-Unanticipated Problems Involving Risk to Subjects or Others
PHI	Protected Health Information
PI	Principal Investigator
SAE	Serious Adverse Event/Serious Adverse Experience
SOP	Standard Operating Procedure
UPIRTSO	Unanticipated Problems Involving Risk to Subjects or Others

3 Study Summary

Title	Feasibility Study of the Kronos Electrocautery Device
Protocol Name	Kronos Study
Protocol Number	SP-01, Version 1.0
Phase	N/A
Methodology	Pilot Study, Non-Randomized
Overall Study Duration (Estimated)	4 months
Subject Participation Duration (Estimated)	14 Days post procedure
Number of Sites	Up to 5
Objectives	The primary objective for this study is to assess safety and performance of the Kronos Electrocautery Device for electrocautery procedures following coaxial biopsy procedures on areas that include, but are not limited to, liver, kidney, lungs, breasts, soft tissue, etc.
Intended Purpose	The Kronos Electrocautery Device is intended to be used in electrocautery procedures to control bleeding by use of electrical current to heat the device probe tip that is applied directly to the target tissue area of treatment.
Study Design	Prospective, multicenter, single arm study with consecutive, eligible subject enrollment at each site. Patients who require a coaxial biopsy procedures on areas that include, but are not limited to, liver, kidney, lungs, breasts, soft tissue, etc., will be eligible to participate in this study.
Number of Subjects	Up to 30 patients
Primary Endpoint	Assess rate of successful electrocautery procedure in absence of procedure related Adverse Events
Inclusion Criteria	
 1. Patients undergoing a scheduled elective coaxial biopsy procedures on areas that include, but are not limited to, liver, kidney, lungs, breasts, soft tissue, etc., 2. Patients have signed an informed consent 3. Patients who are \geq 18 years of age.

Exclusion Criteria	
1. Patients with known bleeding disorder2. Significant congenital anomaly or medical problem that in the opinion of the investigator would preclude enrollment in this study.3. Women of childbearing potential who are pregnant, lactating, or planning to become pregnant during the course of the clinical investigation.4. Active systemic infection or sepsis.
Study Device	Kronos Electrosurgical Device

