8.4.1 When and How to Withdraw Subjects

The patient's participation in this clinical research study is voluntary. If patient decides to take part in this study, he/she will be asked to sign the Informed Consent Form showing that he/she has been informed about the clinical research study. A signed original of the Informed Consent Form will be provided to the patient and a signed second original will be retained in the patient's medical record.

The patient may decide to stop participating in this study at any time. If the patient decides to withdraw from this study, the patient will be asked to participate in a limited capacity allowing the patient's medical status to be followed by telephone contact, medical chart review, or by

other agreed upon method.

If the patient decides not to continue participation in a limited capacity, the doctor will not access patient's medical record or other confidential records for new purposes related to the study; however, study data collected prior to the patient's withdrawal may be reviewed and publicly available records may be consulted prior to or after your withdrawal. If the patient decides to stop taking part in this clinical research study, the patient shall tell his/her study doctor as soon as the patient decides to stop.

The patient's decision to not participate or withdraw or discontinue participation will not result in any penalty or loss of medical care or benefits to which the patient might be otherwise entitled.

The patient's study doctor may end the patient's participation in this clinical research study without the patient's consent. Some of the reasons for ending your participation may be:

The study doctor thinks it is necessary for the patient's health and safety;

1. If the patient becomes pregnant;
2. If the patient does not receive a device;
3. If the patient is unable to keep the his/her scheduled appointments;
4. If the study is stopped by the Sponsor, the Institutional Review Board or by a regulatory authority, such as the FDA.
5. If the patient does not consent to continue in the study after being told of changes in the clinical research study that may affect the patient, or
6. For administrative reasons

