11.1 Sample Size

No formal statistical hypothesis is proposed for this study. A non-statistically driven sample size of 30 patients is considered sufficient for this pilot study.

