12.2 Recording of Adverse Events

At each contact with the subject, the study team must seek information on adverse events by specific questioning and, as appropriate, by examination. Information on all adverse events should be recorded immediately in the source document, and also in the appropriate adverse event section of the electronic case report form (CRF). All clearly related signs, symptoms, and abnormal diagnostic, laboratory or procedure results will be recorded in the source document.

All adverse events occurring during the study period must be recorded. The clinical course of each event should be followed until resolution, stabilization, or until it has been ultimately determined that the study treatment or participation is not the probable cause. Serious adverse events that are still ongoing at the end of the study period must be followed up, to determine the final outcome. Any serious adverse event that occurs during the Adverse Event Reporting Period and is considered to be at least possibly related to the study treatment or study participation should be recorded and reported immediately.

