13.1 Confidentiality

Information about study subjects will be kept confidential and managed according to the requirements of the Health Insurance Portability and Accountability Act of 1996 (HIPAA). Those regulations require a signed subject authorization informing the subject of the following:

- What protected health information (PHI) will be collected from subjects in this study
- Who will have access to that information and why
- Who will use or disclose that information
- The rights of a research subject to revoke their authorization for use of their PHI.

In the event that the subject revokes authorization to collect or use PHI, the investigator, by regulation, retains the ability to use all information collected prior to the revocation of subject authorization. For subjects that have revoked authorization to collect or use PHI, attempts should be made to obtain permission to collect at least vital status (long term survival status that the subject is alive) at the end of their scheduled study period.

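### Section 8.4 lets a patient who withdraws after data completion have data taken out of the data set, adverse events included, and nothing reconciles this with 13.1, 8.4.1 and 12.2 or requires removals to be reported

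*Combined protocol and SAP*

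**What the plan says.** Section 8.4 (Early Withdrawal of Subjects) distinguishes two situations. If consent is withdrawn before the biopsy, no study data are collected. If it is withdrawn after study data are complete, "the participant will need to provide instructions to the study team to remove his/her data from the data set". Adverse event data are not excepted. The same section lists an adverse event among the reasons for discontinuing: "Patient experienced a related or unrelated event that would interfere with the study objectives/evaluation".

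Three other sections bear on data already collected:

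- Section 8.4.1, on patients who decline even limited further participation: "study data collected prior to the patient's withdrawal may be reviewed".
- Section 13.1, on revocation of privacy authorization: the investigator, by regulation, "retains the ability to use all information collected prior to the revocation of subject authorization".
- Section 12.2: "All adverse events occurring during the study period must be recorded".

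The Study Summary gives the primary endpoint as "Assess rate of successful electrocautery procedure in absence of procedure related Adverse Events". The study is single-arm, at up to 5 sites, with descriptive analysis only. On size, section 11.1 states "A non-statistically driven sample size of 30 patients is considered sufficient for this pilot study", section 7.2 gives 30 as a maximum, and section 8.3 states "The study has an accrual target of at least 20 patients". Section 11.2 expects no missing data, imputes none, and does not mention participants whose data have been removed.

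**The concern.** By the time section 8.4 allows a removal request, the patient has been treated and both patient and investigator know how the procedure went. Removal can therefore depend on the outcome. If the patient had a procedure-related adverse event, taking the data out removes a failure from the numerator and a patient from the denominator of the event rate. The reported event rate falls and the reported success rate rises. Because the study has no comparator and no hypothesis test, these observed proportions are its main result.

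Two further weaknesses follow. No section ranks 8.4 against 13.1 when a patient asks for removal, so sites could answer the same request differently. And since the plan has no rule for counting or disclosing removals, a report could follow the protocol and still not show that any had taken place.

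**Working it through.** **Setting the rules side by side**

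| Section | Trigger | Effect on data already collected | Force |
|---|---|---|---|
| 8.4 | Consent withdrawn after data are complete | Removed from the data set if the patient so instructs | Available on request; no adverse event exception |
| 8.4.1 | Patient declines limited participation | Earlier data can be reviewed | Permissive; speaks of review only |
| 13.1 | Privacy authorization revoked | All earlier information can be used | Permissive; a different trigger from 8.4 |
| 12.2 | Any adverse event in the study period | Must be recorded | Mandatory as to recording; silent on later removal |

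Section 13.1 is in the sharpest tension with 8.4, because it covers use of all earlier information. Section 8.4 also has no data rule for a patient who withdraws after the procedure but before the data are complete.

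**Size of the effect**

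The plan offers no figure to reproduce: 30 is stated to have no statistical basis, and no expected event rate is given for the primary endpoint. The event and removal counts below are therefore assumptions. The two values of n, 30 and 20, come from sections 7.2/11.1 and 8.3.

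Let n be patients treated, x those with an event, and d those with an event whose data are removed.

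- Rate with all data kept: x/n
- Rate after removal: (x − d)/(n − d)
- Exact (Clopper-Pearson) 95% limits: lower = Beta quantile 0.025 with parameters (x, n − x + 1); upper = Beta quantile 0.975 with parameters (x + 1, n − x). When x = 0 the lower limit is 0 and the upper limit is 1 − 0.025^(1/n).

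Worked case with x = 1 and d = 1:

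- n = 30: 1/30 = 3.3% (0.1% to 17.2%) becomes 0/29 = 0%, upper limit 1 − 0.025^(1/29) = 11.9%.
- n = 20: 1/20 = 5.0% (0.1% to 24.9%) becomes 0/19 = 0%, upper limit 1 − 0.025^(1/19) = 17.6%.

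If these patients are otherwise successes, the success rate goes from 29/30 = 96.7% to 29/29 = 100%, and from 19/20 = 95.0% to 19/19 = 100%.

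Range at n = 30:

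| Events | Removed | All data kept | After removal |
|---|---|---|---|
| 1 | 1 | 3.3% (0.1 to 17.2) | 0/29 = 0% (0 to 11.9) |
| 2 | 1 | 6.7% (0.8 to 22.1) | 1/29 = 3.4% (0.1 to 17.8) |
| 2 | 2 | 6.7% (0.8 to 22.1) | 0/28 = 0% (0 to 12.3) |
| 3 | 1 | 10.0% (2.1 to 26.5) | 2/29 = 6.9% (0.8 to 22.8) |
| 3 | 2 | 10.0% (2.1 to 26.5) | 1/28 = 3.6% (0.1 to 18.3) |
| 3 | 3 | 10.0% (2.1 to 26.5) | 0/27 = 0% (0 to 12.8) |

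For contrast, removing one patient without an event barely matters: 1/30 = 3.3% becomes 1/29 = 3.4%. The distortion comes from removal that is linked to outcome.

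**The case against.** A reader might infer that following 8.4 means deleting the record of every patient who withdraws late. The text does not say so. Withdrawal alone leaves the data in place; removal takes a separate, explicit instruction from the patient.

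A reader might also infer that the harm itself is erased. Section 8.4 speaks only of the data set. Adverse events also go into source documents (12.2) and onto a worksheet that the site's principal investigator reviews and signs (12.3.1), and events judged to be UPIRTSOs go to the IRB within 5 working days. None of these is said to be erased. This limits the loss to the analysis data set, but that is where the endpoint is computed, and 12.3.1 has the worksheet information entered in the research database too.

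A third tempting reading is that 13.1 and 8.4.1 oblige a site to keep what 8.4 obliges it to delete. Both are permissive, and 13.1 concerns privacy authorization, not study consent. A site could keep data by default and honour a specific removal request without breaching either. What remains is the absence of any stated precedence, not a head-on contradiction.

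Finally, nothing in the documents shows that harmed patients are more likely to complete the study, withdraw and then ask for removal. That is conjecture, the counts above are chosen for illustration, and the intervals before and after removal overlap widely. With no hypothesis, no decision threshold is crossed. All of this stands against a prediction of bias. It does not answer the point that the plan permits outcome-dependent removal and gives no means of seeing it.

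**Conclusion.** The concern holds as a defect in the withdrawal rule. Section 8.4 permits removal on request after the outcome is known, does not except adverse events, is not reconciled with 13.1, 8.4.1 and 12.2, and comes with no reporting of removals. Confidence is high for the wording. The size is conditional: at the study's planned numbers a single removal is enough to replace an observed event rate of 3.3% (n = 30) or 5.0% (n = 20) with zero, and to lower the exact upper limit by 17.2 − 11.9 = 5.3 or 24.9 − 17.6 = 7.3 percentage points. This assumes one patient with an event and removal of that patient's data. The documents do not support saying that such removals will happen, or that the reported rates will be biased by any particular amount. The correction is worth making because it is cheap and the stated primary objective is safety and performance.

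**What to change.** Replace the removal sentence in section 8.4 with a rule consistent with 13.1, for example: data collected up to the time of withdrawal, at any time after the procedure and including adverse events, are retained and analysed as far as consent and applicable regulation allow; no new data are collected without the patient's agreement. This also covers withdrawal between the procedure and data completion. Cross-refer to 8.4.1, 12.2 and 13.1 so that one rule governs at every site.

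Check that the consent form says the same; its text was not available for this review.

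Add to section 11 that the report gives the number and timing of all withdrawals and of any data removals, with device exposure and adverse event status where permitted.

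The cost is one replaced sentence, one reporting line and a check of the consent wording. The real downside is that patients lose, or have limited, the option of having collected data removed. Their right to withdraw is unaffected.

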8.4.1 When and How to Withdraw Subjects

The patient's participation in this clinical research study is voluntary. If patient decides to take part in this study, he/she will be asked to sign the Informed Consent Form showing that he/she has been informed about the clinical research study. A signed original of the Informed Consent Form will be provided to the patient and a signed second original will be retained in the patient's medical record.

The patient may decide to stop participating in this study at any time. If the patient decides to withdraw from this study, the patient will be asked to participate in a limited capacity allowing the patient's medical status to be followed by telephone contact, medical chart review, or by

other agreed upon method.

If the patient decides not to continue participation in a limited capacity, the doctor will not access patient's medical record or other confidential records for new purposes related to the study; however, study data collected prior to the patient's withdrawal may be reviewed and publicly available records may be consulted prior to or after your withdrawal. If the patient decides to stop taking part in this clinical research study, the patient shall tell his/her study doctor as soon as the patient decides to stop.

The patient's decision to not participate or withdraw or discontinue participation will not result in any penalty or loss of medical care or benefits to which the patient might be otherwise entitled.

The patient's study doctor may end the patient's participation in this clinical research study without the patient's consent. Some of the reasons for ending your participation may be:

The study doctor thinks it is necessary for the patient's health and safety;

1. If the patient becomes pregnant;
2. If the patient does not receive a device;
3. If the patient is unable to keep the his/her scheduled appointments;
4. If the study is stopped by the Sponsor, the Institutional Review Board or by a regulatory authority, such as the FDA.
5. If the patient does not consent to continue in the study after being told of changes in the clinical research study that may affect the patient, or
6. For administrative reasons

8.4.2 Data Collection and Follow-up for Withdrawn Subjects

If a participant withdraws from the study, no additional attempts will be made to contact the participant.

9 Study Device

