10.3 Schedule of Events

Study Activity	Schedule of Events		
	Screening/Baseline	Procedure	Follow-up
Informed consent	X		
Medical History	X		
Eligibility criteria	X		
Index data collection		X	X
Adverse event evaluation		X	X

11 Statistical Plan

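### The unconditional no-contact rule in 8.4.2 clashes with 8.4.1 and, in particular cases, with 12.2 and 13.1, and can leave the primary outcome only partly observed

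*Combined protocol and SAP*

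**What the plan says.** Four sections of the combined protocol and SAP govern contact with patients who leave the study.

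- **8.4.2**, headed as the section on data and follow-up for withdrawn subjects, is one sentence with no condition: "If a participant withdraws from the study, no additional attempts will be made to contact the participant".
- **8.4.1** says that on withdrawal "the patient will be asked to participate in a limited capacity allowing the patient's medical status to be followed by telephone contact", or by chart review or another agreed method. If the patient declines, the doctor does not open the medical record for new study purposes, but data already collected may be reviewed. One listed ground for the study doctor to end participation reads: "If the patient is unable to keep the his/her scheduled appointments".
- **12.2** says of AEs: "The clinical course of each event should be followed until resolution, stabilization", or until the study is judged not to be the probable cause. It adds: "Serious adverse events that are still ongoing at the end of the study period must be followed up, to determine the final outcome". Neither sentence makes an exception for withdrawal.
- **13.1** says that for patients who revoked authorization over their health information "attempts should be made to obtain permission to collect at least vital status" at the end of their scheduled study period. It also lets the investigator go on using what was collected before the revocation.

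Section 8.4 adds that a patient who withdraws consent once the study data are complete may instruct the team to take those data out of the data set.

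On the analysis side, the Study Summary gives the primary endpoint as "Assess rate of successful electrocautery procedure in absence of procedure related Adverse Events". The schedule in 10.3 places "Adverse event evaluation" at the procedure and again at follow-up. Section 11.2 expects no missing data, rules out imputation and leaves any missing value as missing.

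**The concern.** Consider a patient who withdraws but agrees to be telephoned. Section 8.4.1 provides for the call and 8.4.2 rules it out. With up to five sites, the question could be settled differently from site to site, and so could the ascertainment of AEs after withdrawal.

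This reaches the primary result. The endpoint requires that no procedure-related AE occurs. A patient who leaves after the procedure with none so far is neither a confirmed success nor a failure. The premise in 11.2, that a study of acute outcomes will have nothing missing, does not cover this case. AE evaluation continues after the procedure day, to 14 days by section 7.3 or 30 days by 12.1.4, and 8.4.1 itself foresees patients who cannot attend. The reported rate then depends on how a few patients are counted. Absence of reintervention, a secondary outcome, is exposed in the same way.

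**Working it through.** **1. The contact rule, by type of patient.**

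- Withdraws and agrees to limited follow-up: 8.4.1 provides for telephone contact and 8.4.2 bars it. This is a direct conflict.
- Withdraws, declines, and has no open AE: 8.4.1 and 8.4.2 agree.
- Withdraws with an unresolved AE or serious AE: 12.2 requires follow-up and 8.4.2 bars contact. The case is foreseeable, because 8.4 lists an AE among the reasons for discontinuing.
- Withdraws and also revokes authorization: 13.1 calls for an attempt to obtain permission. That conflicts with 8.4.2 if the attempt must be made after withdrawal, but not if it is made at the moment of revocation.

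**2. What may be lost.** Section 8.4.2 bars contact, not chart review, but 8.4.1 ties chart review to the patient's agreement. Later AEs, AE outcomes and reinterventions may therefore be lost, mainly in patients who decline. Blood loss and device scores are recorded on the procedure day (10.2) and are not affected by the contact rule.

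**3. Data already collected.** Section 8.4 allows removal on instruction; 8.4.1 and 13.1 allow earlier data to be used. Under removal, even an AE already seen can leave the analysis. With an assumed 3 failures among 30, the rate is 27/30 = 90.0%. Removing one patient with a failure gives 27/29 = 93.1%; removing one with a success gives 26/29 = 89.7%.

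**4. Effect of unknown outcomes on the rate.** There is no plan figure to reproduce: 11.1 says that the 30 is not statistically derived, and no dropout rate is given. Inputs: N = 30 (11.1) or N = 20 (the minimum accrual target in 8.3). The number of unknown outcomes u and of observed failures f are assumptions. Observed successes are s = N − u − f.

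- Available-case rate: s/(N − u)
- Unknowns counted as failures (worst case): s/N
- Unknowns counted as successes (best case): (s + u)/N
- Width of the possible range: u/N, so 1/30 = 3.3 points or 1/20 = 5.0 points per unknown
- Available-case rate too high by at most u·s/(N(N − u)), too low by at most u·f/(N(N − u))

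| N | u | f | Available-case | Worst to best | Too high by up to | Too low by up to |
|---|---|---|---|---|---|---|
| 30 | 1 | 0 | 29/29 = 100% | 96.7–100% | 3.3 | 0 |
| 30 | 3 | 0 | 27/27 = 100% | 90.0–100% | 10.0 | 0 |
| 30 | 3 | 3 | 24/27 = 88.9% | 80.0–90.0% | 8.9 | 1.1 |
| 30 | 3 | 12 | 15/27 = 55.6% | 50.0–60.0% | 5.6 | 4.4 |
| 20 | 3 | 0 | 17/17 = 100% | 85.0–100% | 15.0 | 0 |
| 20 | 3 | 8 | 9/17 = 52.9% | 45.0–60.0% | 7.9 | 7.1 |

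Check of the third row: 3 × 24/(30 × 27) = 72/810 = 8.9 points and 3 × 3/(30 × 27) = 9/810 = 1.1 points, which sum to 3/30 = 10.0 points.

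Exact (Clopper-Pearson) 95% intervals for the second row are 87.2–100% for 27/27 and 73.5–97.9% for 27/30.

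Section 5.1 lists pain, bleeding, burn and scarring each in more than 10% of patients. If these count as procedure-related AEs, the rows with more failures are plausible, and there the error is closer to symmetric.

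**The case against.** The best defence is that 8.4.2 follows directly on 8.4.1 and speaks of additional attempts. That fits a reading in which the request for limited follow-up has already been made and refused. On that reading the clash with 8.4.1 disappears. The reading is reasonable, but the sentence does not state it, and it would not settle 12.2 for a patient who declines with an open AE.

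Second, 11.2 does give a missing-data rule, and an available-case rate follows from it. That stands, so it would be too much to infer that the plan has no rule at all. What 11.2 leaves open is narrower: whether a composite with a known procedure result and truncated AE follow-up counts as missing or is scored on what was seen.

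Third, if the outcomes under Primary Study Outcomes (7.4) govern rather than the Study Summary endpoint, the problem may shrink, since blood loss is measured on the procedure day. That also stands, although 7.4 sets no time window for hematoma or for the need for ultrasound.

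Fourth, the counts are assumed, the study is descriptive and no performance threshold is stated. With one unknown among 30 the whole range is 3.3 points, and the intervals overlap heavily. All of this is correct and limits the weight of the point.

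A reader might also infer that 12.2 and 13.1 contradict 8.4.2 for every withdrawn patient, or that all follow-up ends at withdrawal. The documents do not support either: those conflicts arise only in the cases set out above, and chart review is not barred. Nor is it safe to infer that whatever was seen before withdrawal stays in the data set, given the removal sentence in 8.4.

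**Conclusion.** The point holds as an inconsistency in the text with a modest consequence for the analysis. Section 8.4.2 conflicts with 8.4.1 as written, with 12.2 when an event is unresolved at withdrawal, and with 13.1 when withdrawal and revocation coincide and permission must be sought later. Following 8.4.2 literally may cut AE ascertainment and leave the Study Summary endpoint partly observed. The removal and retention texts are a further unreconciled pair.

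Each unknown outcome widens the possible range by 3.3 points at N = 30 or 5.0 points at N = 20. The number of unknowns is an assumption throughout.

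A tempting stronger reading is that the available-case rate flatters the device. The documents do not establish a direction. Section 8.4 does name an AE as a reason to discontinue, but a procedure-related AE already seen, if its data are kept, is already a failure. It does not show that patients with unknown outcomes fail more often than the others. No hypothesis is tested, so no error rate is affected; the reported rate and the completeness of safety data are.

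**What to change.** (a) Reconcile 8.4.2 with 8.4.1, 12.2 and 13.1, so that the text says which withdrawn patients it covers and what applies to an unresolved AE and to vital status. Reconcile the data-removal sentence in 8.4 with the retention text in 8.4.1 and 13.1.

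(b) In 11.2, state that a patient with truncated AE follow-up and no failure so far has an unknown primary outcome. Report withdrawals, data removals and unknown outcomes by reason. Show the primary rate with unknowns counted as failures and as successes beside the available-case rate. To apply this, the two statements of the primary endpoint (Study Summary and 7.4) and the two follow-up lengths (7.3 and 12.1.4) must also be brought into line, since they decide what counts as truncated.

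The cost is protocol wording and one table, with no additional patients. The sponsor must accept that a less favourable row will be shown: with an assumed three unknowns, up to 10.0 points below the available-case rate at N = 30 and up to 15.0 points at N = 20.
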